5.5.1 Serious Adverse Events Defined

A serious adverse event (SAE) [may also be termed a Serious Suspected Adverse Drug Reaction – Serious SADR; or in device studies, a serious unanticipated device effect – Serious UADE] is defined for this protocol as an adverse event or experience that meets one or more of the following criteria:

- A. A death occurring during the study or which comes to the attention of the Investigator within 6 months of the end of the protocol-defined follow-up period, whether considered treatment-related.
- B. A life-threatening event.
- C. An adverse event requiring in-patient hospitalization or prolonged hospitalization due to the adverse event.
- D. An adverse event resulting in a significant, persistent, or permanent change, impairment, damage or disruption in the participant's body function or structure, physical activities or quality of life. As part of the outcome-measure of these studies, any progression in disease will be identified through routine scheduled visual assessments. Natural progression of disease alone (e.g., worsening of vision) is not to be considered a serious adverse event (SAE). Any disease progression that is deemed by the Investigator as beyond the natural progression of disease will be reported as an SAE.
- E. A congenital anomaly or birth defect, where exposure to the test articles prior to conception or during pregnancy is suspected in resulting in an adverse outcome in the child.
- F. An event that otherwise required a medical or surgical intervention to preclude permanent impairment or damage (excluding unrelated elective or cosmetic procedures).

Hospitalization scheduled before a participant enrolls in the study is not the result of a treatment-emergent AE, and therefore events leading to such hospitalization will not be considered study

AEs or SAEs. During the study, if a participant has elective surgery for a pre-existing condition and the condition did not worsen during the study, the reason for elective surgery (and resulting hospitalization, if applicable) should not be considered or reported as an SAE. Surgery or hospitalization should always be reported as an outcome of an adverse event. In the case of surgery for a pre-existing condition, the surgery or hospitalization itself does not merit an SAE report.

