6.6 Interim Monitoring

The SMC will review safety summaries on a periodic basis throughout the trial. Data summaries will be provided by the study statistician in advance of all SMC meetings.

7 Human Participant Protection

All participants will receive a verbal explanation by the Principal Investigator or qualified designee, or as designated by state or local law in terms suited to their comprehension of the

purposes, procedures, and potential risks of the study. The participants must have the ability to understand and sign an informed consent form, which must be obtained prior to enrollment. The participants will have an opportunity to carefully review the consent and ask questions regarding this study prior to signing, and they will be informed that they may withdraw from the study at any time without prejudice to themselves.

The participants' names will not appear on any of the data forms reported to the sponsor. Participants will be identified by a name code and a study registration number. The information collected will remain confidential.

There are risks associated with the examination procedures required for participants in this study. However, these are all standard procedures that are performed as part of a normal eye and medical exam. The procedures associated with the implant/explant of the device employ standard surgical techniques but the device itself is experimental. Some of the discomforts associated with the ocular exam include the following:

1. Dilating drops or anesthetic drops may sting. They can cause an allergic reaction, or if contaminated, can cause an infection, but neither of these problems is very likely to occur.
2. Dilating drops can also cause a sudden increase of pressure (acute glaucoma) in eyes that are already predisposed to develop this condition. There is little risk of glaucoma being triggered in this way, but if it is, treatment is available.
3. In rare instances, the cornea may be abraded during measurement of intra-ocular pressure or use of a contact lens (used for examination purpose only and not a contact lens used to correct one's refractive error). A corneal abrasion of this sort may be painful, but it heals quickly with no lasting effects.

There are also risks associated with the surgeries to implant and explant the device and with the sham surgery. In general, the risks of intra-ocular surgery are very small and are described below.

8 Study Risk and Precautions

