8.4 IOP Examination and ERG

In rare instances, the cornea may be abraded during measurement of intra-ocular pressure or use of a contact lens electrode. An abrasion like this may be painful, but it heals quickly with no lasting effects. In the event that a participant experiences a corneal abrasion, ointment should be administered and an eye patch or gauze should be placed over the eye.

9 Confidentiality and Access to Source Documents and Data

The Investigators and study staff must maintain the highest degree of confidentiality permitted for the information obtained from participants in this clinical study. Although medical and research records should be maintained in the strictest confidence, as part of the quality assurance and legal responsibilities of an investigator, the site must permit authorized representatives of the sponsor, SMC, and regulatory agencies to examine (and when permitted or required by applicable law, to copy) clinical records for the purposes of quality assurance reviews, audits and

evaluation of the study safety and progress. Unless required by the law, no copying of records with personally identifying information will be permitted. Only the coded identity associated with documents or other participant data may be copied (obscuring any personally identifying information) or transmitted to the sponsor. Authorized representatives as noted above are bound to maintain the strict confidentiality of medical and research information that may be linked to identified individuals.

10 Summary of GCP Compliance

This trial will be conducted in accordance with Good Clinical Practice (GCP) using the guidance documents and practices offered by ICH and FDA, and in accordance with the Declarations of Helsinki. This study will also comply with the regulations under 21 CFR Parts 50, 54, 56, and 312 under an IND application authorized by FDA.

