7.7.2 Adverse Events

7.7.2.1 Individual events

The proportion of subjects with at least one of the following safety-related events will be compared using Fisher's Exact Test. Non-serious adverse events (not requiring narrative form) are listed here: irritation or infection from dilation drops, bruising from blood work.

Serious ocular adverse events (which must be reported within 24 hours and which require a narrative form) are listed here: acute angle closure glaucoma precipitated by dilation, corneal abrasion after tonometry or electroretinography, risks associated with implantation surgery (cataract, retinal detachment, infection, bleeding).

In addition, we will compare the rate of each of the adverse events during the follow-up period using Poisson regression, which can take into account multiple instances of adverse events within a single subject.

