7.7.2.2 Pooled adverse events

Adverse events will be analyzed according to four main categories:

- Proportion of subjects with *any ocular adverse event*
- Proportion of subjects with *any serious ocular adverse event*
- Proportion of subjects with *any non-ocular serious adverse event*
- Proportion of subjects with *any non-ocular adverse event*

The proportion of subjects with these events will be compared between the arms using Fisher's Exact Test. Poisson regression will be applied to compare the rates of overall adverse events, including recurrent events.

8 Reporting conventions

- All tables and data listings will be presented in landscape orientation, unless presented as part of the text of the final report.
- Figures will be presented in landscape orientation, unless the information is substantially easier to interpret in portrait orientation.
- Direct annotation of figures will be preferred to legends. All figures with more than one variable or item will contain either direct annotation or legends. All annotation will be unambiguously identifiable as such.
- Color will be used in figures only when needed to enhance clarity of communication. All color schemes will be evaluated for visual clarity for individuals with diminished color vision. All color encodings will be identified. Redundant encodings (such as the use of different plot symbols or line dash patterns) will be used in addition to color, so that all figures are interpretable after monochrome reproduction at 100 dots per inch. All dash patterns and line widths will be adequate to be distinguishable after monochrome reproduction at 100 dots per inch. Any distinction between plot symbols (circles, filled circles, diamonds, etc.) will remain clear after monochrome reproduction at 100 dots per inch.

- Sans serif fonts will be used for all labeling (Helvetica, Arial, Futura, or Computer Modern Sans Serif (CMSS)).
- Boldface and italics will not be used unless substantial value is added.
- Decorative fonts and enhancements, including borders and shading, will not be used. Decorative presentation methods, such as ribbon graphs, will never be used.
- All information given in figures will also be presented in summary tables (perhaps only included in an Appendix or in supplementary materials).
- Only standard characters will be used in tables and data listings.

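### SAP 7.7.2.1 makes named ocular events serious by type, against the outcome-based definition in Protocol 5.5.1, so the pooled serious-event comparison would probably miscount

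*SAP*

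**What the plan says.** SAP 7.7.2.1 has a short non-serious list: "irritation or infection from dilation drops, bruising from blood work". The other list opens with "Serious ocular adverse events (which must be reported within 24 hours and which require a narrative form) are listed here". It contains angle-closure glaucoma precipitated by dilation, and then "corneal abrasion after tonometry or electroretinography, risks associated with implantation surgery (cataract, retinal detachment, infection, bleeding". Neither list sets a condition on severity, duration or outcome.

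SAP 7.7.2.2 then pools events into four categories, one of which is the proportion of subjects with "any serious ocular adverse event", and compares the arms by Fisher's exact test. The SAP neither refers to Protocol 5.5.1 nor defines a serious event in any other way.

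Protocol 5.5.1 says that a serious adverse event "is defined for this protocol as an adverse event or experience that meets one or more of the following criteria". The criteria are death (A), threat to life (B), hospitalization (C), significant or lasting impairment (D), birth defect (E), and a residual category (F): "An event that otherwise required a medical or surgical intervention to preclude permanent impairment or damage".

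On the expected course of the listed events, Protocol 8.4 says of corneal abrasion: "An abrasion like this may be painful, but it heals quickly with no lasting effects". Protocol section 7 says the same. Protocol 8.1 describes infection and bleeding after implant surgery as mostly short-lived, clearing in about two weeks, and Protocol 4.1 is similar.

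**The concern.** The two documents use the word serious for different sets of events. An abrasion that heals in days, or a small conjunctival bleed, would normally meet none of criteria A to F, yet the SAP list calls it serious. If that list defines the pooled category, the final report would present a serious-event proportion that cannot be matched to the SAE forms collected under Protocol 5.3.1.

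Serious events also carry weight during the trial. SAP 6.2.3 singles them out among the endpoints examined when stopping for harm is considered, and has them sent to the SMC Chair. Two definitions would leave the committee and the report with different counts.

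The reporting rules diverge as well. The SAP attaches a 24-hour report and a narrative to every listed item. Protocol 5.3 and 5.5 allow expected, non-serious events to be recorded routinely on case report forms.

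**Working it through.** The documents state no serious-event rate or count, so there is no figure of the plan to reproduce. The check is a comparison of text, followed by an illustration under assumed rates.

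**1. Listed items against Protocol 5.5.1**

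| SAP serious item | What the Protocol says | Criterion A-F met? |
|---|---|---|
| Corneal abrasion | Heals quickly, nothing lasting (section 7, 8.4) | Normally none |
| Surgical bleeding | Small amount, usually temporary (4.1, 8.1) | Normally none if minor |
| Surgical infection | Usually temporary; more serious cases may need surgery and implant removal (4.1, 8.1) | Depends on the case; D or F possible |
| Cataract | Named as a possible side effect (4.1) | Depends on the case; F possible if surgery is needed |
| Retinal detachment, angle closure | Named as possible | D or F plausible |

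The SAP lists do not sort by outcome. Infection from dilating drops is non-serious and infection from implantation surgery is serious, whatever course either takes.

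**2. Which eye is affected**

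Only the implant eye has a 2.0 mm sclerotomy; the sham eye has pressure on the sclera (Protocol 4.6.1). But both eyes have a conjunctival peritomy and suture closure, and Protocol 4.1 attributes risks to the sham surgery too. Abrasion from tonometry or ERG is not tied to either eye.

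**3. Illustration**

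All rates here are assumptions. For one eye let a be the chance of an examination-related abrasion (same in both eyes), b the chance of a minor listed surgical event, and s the chance of an event meeting Protocol criteria. Then

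P(serious by the SAP list) = 1 - (1 - a)(1 - b)(1 - s).

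Take s = 5% for implant and 2% for sham eyes, and n = 20 eyes per arm (SAP 3.1.5). Under the Protocol definition the expected counts are 20 × 0.05 = 1.0 and 20 × 0.02 = 0.4, a difference of 0.6 and a ratio of 2.5.

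Worked example, row (i), implant eye: 1 - 0.95 × 0.90 × 0.95 = 0.188, times 20 = 3.8. Sham eye: 1 - 0.95 × 0.95 × 0.98 = 0.116, times 20 = 2.3.

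| Row | a | b implant / sham | Expected eyes, implant vs sham | Difference | Ratio |
|---|---|---|---|---|---|
| Protocol definition | - | - | 1.0 vs 0.4 | 0.6 | 2.5 |
| (i) | 5% | 10% / 5% | 3.8 vs 2.3 | 1.4 | 1.62 |
| (ii) | 5% | 30% / 10% | 7.4 vs 3.2 | 4.1 | 2.27 |
| (iii) | 10% | 50% / 10% | 11.5 vs 4.1 | 7.3 | 2.78 |
| (iv) | 10% | 50% / 50% | 11.5 vs 11.2 | 0.3 | 1.02 |

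Differences are taken before rounding the counts. Counts rise in both arms in every row. The difference grows in (i) to (iii) and shrinks in (iv). The ratio falls in (i), (ii) and (iv) and rises only in (iii).

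**4. How few events matter**

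With Fisher's exact test, two-sided 0.05 (SAP 3.1.1), significance needs at least 5 of 20 implant eyes against 0 of 20 sham, or 11 against 4. With 30 per arm (Protocol section 4 gives about 30 participants) it needs 6 against 0, or 12 against 4. A handful of reclassified minor events could therefore create or remove a nominally significant result.

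**The case against.** Several points on the other side are fair.

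- **The link between the sections is not stated.** SAP 7.7.2.2 does not say that its serious category is the 7.7.2.1 list; an analyst could take seriousness from the SAE forms. This stands as a caveat. But the list is headed as serious ocular events, it comes directly before the pooled category, and the SAP offers nothing else, so the list is the natural reading.
- **Not every listed event is over-counted.** Retinal detachment, angle closure, serious infection or cataract needing surgery can meet D or F. This stands. The clear over-counts are abrasion and minor bleeding or infection. One might argue that an abrasion given ointment and a patch (Protocol 8.4) meets F, but F requires that the intervention be needed to avert permanent damage, and the Protocol expects none.
- **The consequence is limited.** The SAP also compares events individually, sends SAEs to the SMC Chair with a narrative, and says that safety will not be judged on tests alone (7.4, 7.5.2). No efficacy result is affected. This lowers the stakes but does not remove the miscount.

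Two stronger inferences are tempting and are not supported. The first is that the miscount falls mainly on implant eyes. That is plausible for intraocular events, because only that eye is opened, but it does not follow for abrasion or superficial bleeding, and no rates are given; row (iv) shows dilution instead. The second is that the list would put the trial at odds with the sponsor's 15-day FDA reports. Under Protocol 5.4 those cover only events that are associated with the test article and are both serious and unexpected, so they would differ from any SAE table under either definition.

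**Conclusion.** Wrong as written, in a safety table and not in the efficacy analysis. SAP 7.7.2.1 classes events as serious by type; Protocol 5.5.1 does so by outcome or required intervention; the SAP does not say which governs 7.7.2.2. If the list governs, minor transient events are counted as serious and the category disagrees with the recorded SAEs.

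The effect on the implant-versus-sham contrast cannot be sized or signed from the documents. It could be inflated if minor surgical events are more frequent in implant eyes, or diluted if they are equally frequent. The illustrative range, 0.3 to 7.3 eyes against 0.6, rests entirely on the assumed rates. The conclusion that the definitions conflict does not depend on them.

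**What to change.** In SAP 7.7.2, state that an event is serious if the investigator recorded it as meeting a criterion in Protocol 5.5.1, and that the serious categories in 7.7.2.2 use that record. Relabel the named items in 7.7.2.1 as ocular events of interest and tabulate them by eye, whether or not each was serious. SAP 7.7 already names the McNemar test for comparing the two eyes. Reconcile the SAP's 24-hour and narrative requirement for listed items with the reporting routes in Protocol 5.3 and 5.5.

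The cost is SAP wording and one extra table row. No new data should be needed, because Protocol 5.3.1 already requires an SAE form for each serious event.

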6.1 Description of Trial

10 subjects will be enrolled into the study. Both eyes of each participant will be evaluated in this study. There are, thus, a minimum of 10 participants and a minimum of 20 eyes in the trial. One eye of each participant will be randomly assigned to receive CNTF, and the fellow eye will receive sham surgery. AOSLO montages will be acquired at baseline 1 covering the central 5.7 degrees to identify at least 7 ROIs where unambiguous cone mosaics are visualized. AOSLO images will be acquired at Baseline 2 within 1 month of Baseline 1 and focused on the ROIs. Humphrey visual field sensitivity of each eye will be measured at baseline, month 6, month 12, month 18, month 24 and month 30. The total score for the entire retina, averaged across replicates, will serve as the unit of analysis for baseline qualifications and efficacy outcomes. In addition, the 5 points of the visual field with the greatest change during treatment will serve as a key secondary efficacy variable. Pupil size will be recorded during HVF assessment.

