3.1 Sample Size Planning

3.1.1 Alpha level

The study hypotheses are listed as bidirectional effects; we will never conduct one sided tests. All hypothesis tests proposed for the CNTF Implant Trial are two-sided.

Results will be judged significant using a two-tailed α of 0.05.

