7.5.2.7 Other outcomes

For the incidence of adverse events following application of the investigational product in all subjects, we propose to use Poisson or negative binomial random-effects regression (extending to a more general hidden Markov model in the event of poor fit of the simpler models). Specifically, we will test the hypothesis that the underlying event rate per unit time is the same in the treatment and sham eyes. As a secondary analysis, we will analyze the time to first adverse event in each group using Cox proportional hazards regression (using baseline medical history as well as time since last treatment as covariates). We emphasize that while the statistical fit may be informative, decisions about drug safety (or trial continuation) will not be based solely on statistical criteria.

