7.7 Safety and tolerability

The analysis of safety in this study will include summaries of the following:

- Exposure
- Adverse events
- Adverse events and serious adverse events
- Adverse events leading to withdrawal
- Any deaths

The incidence of adverse events will be compared between treatment and sham eyes using the McNemar test.

Additional considerations are given in §7.4.

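### The SAP names two different rate models for recurrent adverse events; the plain Poisson version makes no allowance for eye-specific clustering and can overstate significance when events are frequent

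*SAP*

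**What the plan says.** The design is paired. Protocol 6.1 states: "One eye of each participant will be randomly assigned to receive CNTF, and the fellow eye will receive sham surgery". The SAP then describes the comparison of adverse events in several places.

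- **SAP 7.5.2.7 (Other outcomes):** "we propose to use Poisson or negative binomial random-effects regression", with a hidden Markov model as the fallback if those models fit badly. The hypothesis is explicit: "we will test the hypothesis that the underlying event rate per unit time is the same in the treatment and sham eyes".
- **SAP 7.7 (Safety and tolerability):** "The incidence of adverse events will be compared between treatment and sham eyes using the McNemar test".
- **SAP 7.7.2.1 (Individual events):** after a Fisher test on the proportion with at least one event, the rate of each event is compared "using Poisson regression, which can take into account multiple instances of adverse events within a single subject".
- **SAP 7.7.2.2 (Pooled adverse events):** "Poisson regression will be applied to compare the rates of overall adverse events, including recurrent events". The categories listed there include both ocular and non-ocular events.

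Neither 7.7.2.1 nor 7.7.2.2 names a random effect, a dispersion term, a clustered variance or the pairing of eyes. Neither refers back to 7.5.2.7. The general significance rule is in SAP 3.1.1: "Results will be judged significant using a two-tailed α of 0.05".

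**The concern.** Two specifications stand for one question, and no order of precedence is given. If they disagree, the analyst chooses after seeing the data which rate ratio and p-value to report. That much needs no assumption about event rates.

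The second issue is what plain Poisson regression leaves out. It takes the variance of a count to equal its mean. Only one eye has a sclerotomy and an implant, and the complications listed in Protocol 4.1, such as infection, inflammation and fibrosis, arise in a particular eye and may recur there. If a few eyes contribute many events, the count varies more than the model allows and the standard error of the rate ratio is too small. An apparent excess or deficit in implant eyes could then be the work of a handful of eyes. Safety is one of the two stated objectives (SAP 2.3.1), so a misleading interval in either direction matters.

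**Working it through.** **Inputs from the documents.** Two-sided alpha 0.05 (SAP 3.1.1). One implant eye and one sham eye per person (Protocol 6.1). SAP 3.1.5 gives 17 people, or 20 after 15% loss: 17 / 0.85 = 20. Protocol 6.1 gives 10 and Protocol section 4 about 30. No document gives an adverse-event rate, a dispersion or an error rate for the Poisson comparison, so the plan has no figure of its own to reproduce here. Event rates and variances below are assumptions.

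**Step 1: what enters the contrast.** Let the count in eye j of person i be Poisson with mean μ·P_i·E_ij. P_i is a person effect with mean 1 and variance v_p, shared by both eyes. E_ij is an eye effect with mean 1 and variance v_e. With no treatment effect, the within-person difference has variance

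2μ + 2μ²·v_e·(1 + v_p) = 2μ·φ, where φ = 1 + μ·v_e·(1 + v_p).

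Plain Poisson assumes 2μ. If v_e = 0, then φ = 1 whatever v_p is: shared clustering cancels. Only eye-specific variation inflates φ.

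**Step 2: large-sample size of the nominal 5% test.** Size = 2·(1 − Φ(1.96/√φ)). With v_p = 0.5:

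| μ per eye | v_e | φ | 1.96/√φ | Large-sample size | Simulated Wald size, 20 pairs |
|---|---|---|---|---|---|
| 1 | 0 | 1.00 | 1.960 | 5.0% | 4.5% |
| 1 | 0.5 | 1.75 | 1.482 | 13.8% | 12.5% |
| 1 | 1 | 2.50 | 1.240 | 21.5% | 19.9% |
| 2 | 0 | 1.00 | 1.960 | 5.0% | 4.9% |
| 2 | 0.5 | 2.50 | 1.240 | 21.5% | 20.7% |
| 2 | 1 | 4.00 | 0.980 | 32.7% | 30.8% |

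The simulation used 20,000 trials per setting, gamma effects and no true difference. The test was a Wald test on log(A/B) with standard error √(1/A + 1/B), where A and B are the total events in implant and sham eyes. This is the Poisson regression estimate under equal exposure. With 10 or 30 pairs, eye-level clustering in the same range gave 11-31%, so the differing sample sizes do not change the picture.

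**Step 3: shared clustering only.** With v_e = 0, v_p of 1 to 2 and 1 to 4 events per eye (20 pairs), Wald size was 4.6-5.1%. In fitted Poisson models at 1 event per eye, the mean standard error and the true standard deviation of the log rate ratio were both 0.330 with shared variance 1. With eye-specific variance 1 instead they were 0.333 and 0.481.

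**Step 4: rare events.** At 0.2 events per eye with 20 pairs, v_p = 0.5 and v_e from 0 to 1, Wald size was 1.1-2.3%. The large-sample formula does not apply at so few events. The direction also depends on the test: over a range of variance settings at this event rate, a likelihood-ratio test gave 7.6-13.1%. The SAP does not say which test is meant.

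**Step 5: candidate replacements, 20 pairs.**
- A paired t-test on the within-person count difference stayed at 3.9-5.0% in the step 2 settings.
- Poisson with variance clustered on person and a t reference gave 5.9% (μ = 1) and 6.2% (μ = 2) with eye-level variance 1 and no shared effect. With a shared variance of 1 as well, it gave 9.0% and 9.5%, still well below plain Poisson at 22.5% and 34.4%.
- A sign-flip permutation test gave 0.1-4.6% in runs that included sparse events: valid but conservative.
- The negative binomial option was not simulated.

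**The case against.** The clause in 7.7.2.1 follows a Fisher test on at least one event. Read in that setting, it says only that a rate model uses the repeats which Fisher's test discards. That is true. A reader might infer that the SAP claims Poisson regression handles dependence among repeat events, and so rests on a false statement. The wording does not require that reading.

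A reader might also infer that the adverse-event rate comparison will have error rates several times 5%. The documents do not support that, because they give no event rate or dispersion. Clustering within a person, which the clause brings to mind, does no harm in this paired contrast. Several events listed in 7.7.2.1, such as angle-closure glaucoma or retinal detachment, are unlikely to recur often in one eye, and at low rates the Wald test is conservative.

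Finally, the SAP has safeguards. SAP 7.5.2.7 plans a richer model for the same hypothesis and says safety decisions will not rest on statistics alone. SAP 7.7 adds a paired McNemar test, 7.6.3 requires checks of model adequacy, and 7.4 says that failure to find harm does not show safety.

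All of this limits the consequence. It does not settle which rate model governs. Nor does it make plain Poisson suitable for pooled ocular events, where counts per eye are likely to be highest.

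**Conclusion.** The point holds in a limited form. The firm finding is an unreconciled specification: 7.7.2.1 and 7.7.2.2 name plain Poisson regression, 7.5.2.7 names a random-effects or negative binomial model for the implant-versus-sham rate hypothesis, and no rule chooses between them.

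The error inflation is conditional. It needs variation specific to an eye and fairly frequent events. Under assumed eye-level variances of 0.5-1, a shared person variance of 0.5 and 1-2 events per eye, the nominal 5% Wald test rejects in roughly 12-31% of trials with no true difference. With only shared clustering it holds at about 5%, and at 0.2 events per eye it falls to about 1-2%. The exposure is therefore mainly in the pooled ocular comparison of 7.7.2.2. The change is worth making because it is cheap, not because a false safety signal has been shown to be likely.

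**What to change.** 1. In SAP 7.7.2.1 and 7.7.2.2, replace the plain Poisson regression by a reference to one governing model in 7.5.2.7.
2. In 7.5.2.7, state that model so that it handles both pairing and eye-level overdispersion. Options are a negative binomial model with a person effect, or Poisson regression with variance clustered on person and a small-sample t reference. A person random intercept alone is not enough, because it leaves eye-specific variation untouched. Note that the clustered variance can remain somewhat above 5% at this sample size.
3. Where events are too few to fit the model, use a sign-flip permutation test on the within-person difference in counts, and say that it is conservative with few events. Define in advance what counts as too few.
4. Limit the between-eye rate comparison to ocular events. Non-ocular events belong to neither eye and can be summarised descriptively.
5. Reword the clause in 7.7.2.1 to say only that the rate model counts repeat events.

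The cost is SAP wording and one changed model call. Confidence intervals for adverse-event rate ratios will be somewhat wider.
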